6.1.1. Belantamab Mafodotin Treatments Administered

Belantamab mafodotin will be administered to participants intravenously as mg/kg calculated dose at the study site. The dose to be administered will be calculated using actual body weight at baseline and may be reduced for toxicity according to protocol guidelines. It is recommended to prime the IV tubing with at least 15 mL prior to dosing. Administration of belantamab mafodotin will be documented in the clinic source documents and reported in the electronic case report form (eCRF). The time of start and end of infusion will be documented in eCRF.

Belantamab mafodotin will be administered on Day 1 of each cycle over approximately 30-60 minutes. Premedication is not required prior to infusion unless deemed medically necessary by the investigator, in which case it should be administered according to institutional recommendations.

Any participant experiencing an IRR must receive appropriate medical treatment. When the participant's condition is stable, the infusion may be restarted at a slower rate. For details on restarting the belantamab mafodotin infusion after interruption for IRR, please see Table 4.

In general, upon restarting, the infusion rate must be decreased by half at the time the infusion was interrupted.

Participants will be treated until disease progression, or until unacceptable toxicity (Section 7).

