6.6. Dose Modification

Table 4 details the permitted dose modifications of belantamab mafodotin. Table 5 and Table 6 contain dose modification guidance for drug-related AEs. See Table 7 for dose modification guidelines for belantamab mafodotin treatment-related changes in vision.

Table 4 Permitted Dose Reductions

Starting dose	Dose reduction
2.5 mg/kg	1.9 mg/kg
3.4 mg/kg	2.5 mg/kg, 1.9 mg/kg

If the participant cannot tolerate the drug after the allowed dose reduction of belantamab mafodotin to the lowest allowed dose of 1.9 mg/kg, he or she must discontinue treatment for lack of tolerability.

In case of full resolution of symptoms which lead to dose reduction, further treatment at the previous dose level may be considered by the investigator.

If a dose is delayed, the participant should wait for the next scheduled dose to resume treatment. In individual cases where in the judgment of the Investigator waiting a full cycle to resume treatment after delay (skipping dose) related to toxicity which has resolved would be detrimental to the participant's health, the PI should contact the Medical Monitor to discuss an earlier re-start. An earlier re-start may be considered only for participants who have recovered from toxicity to at least ≤Grade 1. The dosing with belantamab mafodotin cannot occur more frequently than every 21 days (±3-day

window). In such cases, efficacy and safety assessments must remain every 3 weeks in line with initial efficacy and safety assessments on study, which may result in 2 separate visits (1 for dosing, 1 for disease assessments). Evaluations associated with a dose would be entered into the eCRF under the next scheduled cycle.

Resuming treatment with belantamab mafodotin will be possible with or without dose reduction after the toxicity has resolved to Grade 1 or less.

Table 5 Dose Modification Guidelines for Belantamab Mafodotin-Related Adverse Events

Toxicity	Grade/description of toxicity	Recommendations for Belantamab Mafodotin
Elevated serum creatinine which cannot be explained by concomitant sepsis, TLS, other severe condition with fever, or dehydration	If absolute serum creatinine increases from baseline by >0.5 mg/dL	 Repeat serum creatinine within 48 hours If confirmed: withhold therapy, institute treatment and monitoring as clinically indicated, and follow for resolution Discuss any further dosing with Medical Monitora

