Neutropenia	Grade ≥3 Defined as ANC <1.0x10 ⁹ /L	 If noted on Day 1 of any cycle, withhold belantamab mafodotin. Consider more frequent hematology (CBC) monitoring as clinically indicated, until recovery to Grade 2 or less. Resume belantamab mafodotin at pre-held dose once neutropenia recovers to Grade ≤ 2 (ANC ≥ 1.0x10⁹/L) on Day 1 of the subsequent cycle. Prophylactic antibiotics, per physician discretion and local institutional guidance. Consider growth factors. Local guidance must be followed for hematological monitoring, if more conservative than the protocol SoA specifications. In cases of frequent recurrent neutropenia (ANC <1.0x10⁹/L), consider dose reduction of belantamab mafodotin by 1 level
	2	Stop the infusion, provide medical treatment and continue at half the original infusion rate after resolution to Grade 0-1. Any future infusion needs to be pre-medicated.
Infusion Reaction ^b	3	 Further treatment with belantamab mafodotin needs to be discussed with Medical Monitor. Continuation only allowed after recovery to ≤Grade 1 and with pre-medication, and extension of infusion time to 2-4 hours. Any future infusion needs to be pre- medicated.
	4	Permanently discontinue from study treatment
Pneumonitis	2	 Withhold treatment with belantamab mafodotin Upon recovery, restart treatment with 1 dose level reduction. If patient is already at the lowest dose level (1.9 mg/kg), then rechallenge with the same dose must be discussed with the Medical Monitor
	Grade 3-4	Permanently discontinue from treatment

a. Medical Monitor may consult GSK's nephrotoxicity panel about plans to continue therapy.

b. If symptoms resolve within one hour of stopping infusion, the infusion may be restarted at 50% of the original infusion rate (e.g., from 100 mL/hr to 50 mL/hr). Otherwise dosing will be held until symptoms resolve and the participant must be pre-medicated for the next scheduled dose.

Table 6 General Dose Modification and Management Guidelines for Drugrelated Adverse Events Not Otherwise Specified

Severity	Management	Follow-up
Grade 1	 Administer symptomatic treatment as appropriate Continue study drug(s)^a 	Provide close follow-up to evaluate for increased severity, no dose modification necessary

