7.1.2. Allergic and Anaphylactic Reaction Stopping Criteria

All participants will be monitored carefully for evidence of allergic response. A participant that exhibits signs or symptoms of severe hypersensitivity or anaphylaxis will receive appropriate medical treatment and permanently discontinue study treatment but will continue in the study.

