8. STUDY ASSESSMENTS AND PROCEDURES

A signed, written informed consent form must be obtained from the participant prior to any study-specific procedures or assessments being performed. The timing of each assessment is listed in the Schedule of Activities (Table 1).

A list of clinical laboratory tests is displayed in Appendix 2.

Whenever vital signs, 12-lead electrocardiograms (ECGs) and blood draws are scheduled for the same nominal time, the assessments must occur in the following order: 12-lead ECG, vital signs, blood draws. The timing of the assessments must allow the blood draw to occur at the exact nominal time. Detailed procedures for obtaining each assessment are provided in the SRM.

- Study procedures and their timing are summarised in the SoA.
- Protocol waivers or exemptions are not allowed
- Immediate safety concerns should be discussed with the sponsor immediately upon occurrence or awareness to determine if the participant should continue or discontinue study treatment.
- Adherence to the study design requirements, including those specified in the SoA, is essential and required for study conduct.
- All screening evaluations must be completed and reviewed to confirm that potential participants meet all eligibility criteria. The investigator will maintain a screening log to record details of all participants screened and to confirm eligibility or record reasons for screening failure, as applicable.
- Procedures conducted as part of the participant's routine clinical management (e.g., blood count) and obtained before signing of ICF may be utilised for screening or

baseline purposes provided the procedure met the protocol-specified criteria and was performed within the time frame defined in the SoA.

• Visit Windows:

- Baseline disease assessments must be completed with 21 days prior to dosing start unless otherwise specified. Refer to SoA.
- Screening assessments performed within the permitted time do not need to repeated on C1D1 unless otherwise specified.
- Safety labs completed within 72 hours of first dose do not need to be repeated on C1D1.
- Pregnancy testing must be completed within 72 hours prior to first dose.
- An ECHO completed within 3 months prior to screening can be used as a screening value.
- Imaging applicable for participants with extramedullary disease must be completed within 30 days prior to first dose.
 - On study visits have a ± 3 -day window and PD follow-up visits have a ± 7 -day window.

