8.3.8. Adverse Events of Special Interest

Adverse events of special interest (AESI) for belantamab mafodotin are corneal events, thrombocytopenia and infusion related reactions. The severity of all AESI will be graded utilizing the National Cancer Institute- Common Toxicity Criteria for Adverse Events. Severity of corneal events will also be graded using the scale provided in Table 7. Guidelines for dose modifications and interruptions for management of common toxicities associated with the study treatment(s) are provided in Table 4. Dose modifications for belantamab mafodotin corneal events will be based on the GSK scale for corneal events in Table 7.

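### Table 5 footnote b and Section 6.1.1 give a half-rate restart with no grade limit, which conflicts with the Grade 3 infusion-reaction row; 6.1.1 also cites the wrong table

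*Protocol*

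**What the plan says.** Protocol Section 6.6, Table 5, has one Infusion Reaction entry covering Grades 2, 3 and 4.

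- **Grade 2:** stop, treat, and continue at half the rate once the reaction is Grade 0 or 1.
- **Grade 3:** further treatment must be discussed with the Medical Monitor. "Continuation only allowed after recovery to ≤Grade 1 and with pre-medication, and extension of infusion time to 2-4 hours". A separate sentence requires premedication before any later infusion.
- **Grade 4:** permanent discontinuation, repeated in Section 7.1.4.
- **Footnote b**, attached to the entry's label and not to one grade: "If symptoms resolve within one hour of stopping infusion, the infusion may be restarted at 50% of the original infusion rate". If symptoms last longer than an hour, dosing is held and the next scheduled dose must be premedicated.

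Section 6.1.1 covers any participant with an infusion-related reaction (IRR). Once the participant is stable, the infusion may be restarted more slowly: "In general, upon restarting, the infusion rate must be decreased by half at the time the infusion was interrupted". It then directs the site elsewhere: "For details on restarting the belantamab mafodotin infusion after interruption for IRR, please see Table 4". The table cited there is "Table 4 Permitted Dose Reductions", which lists only the dose levels to which a participant may be reduced.

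Section 8.3.8 names IRR as one of three adverse events of special interest and states: "Guidelines for dose modifications and interruptions for management of common toxicities associated with the study treatment(s) are provided in Table 4". Sections 6.6 and 7.1.4 point correctly to Table 5 (6.6 also to Table 6).

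**The concern.** A site managing a Grade 3 reaction at the bedside has two instructions for the same infusion. One sets conditions specific to Grade 3. The other depends only on symptoms resolving or the participant being stable, and then halves the rate. No text says which prevails on the day.

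Footnote b's symptom resolution largely covers the row's recovery to Grade 1 or less. Three elements are left unsettled for a same-day restart: Medical Monitor discussion, premedication and infusion time. A site that took footnote b or 6.1.1 as the same-day rule could restart without any of them. Section 6.1.1, which governs administration, cites a table that has nothing on restarting an infusion.

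**Working it through.** The plan gives no figure of its own here. The check compares the texts and then asks whether one restart could satisfy both rules.

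**Texts side by side**

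- At Grade 2, the row, footnote b and 6.1.1 all give half rate. At Grade 4, the row and 7.1.4 both end treatment. The conflict is therefore at Grade 3 only.
- The Grade 3 row does not say whether continuation includes the interrupted infusion. Its structure suggests that it does. Future infusions have their own sentence, and the Grade 2 row, built the same way, uses the verb for the interrupted infusion.

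**Arithmetic**

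Inputs: planned time T = 30 to 60 min (6.1.1); restart at 50% of the rate (footnote b); Grade 3 infusion time of at least 120 min (Table 5). The fraction f given before the stop is not in the documents and is varied.

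- Whole infusion after a half-rate restart = fT + (1−f)T/0.5 = T(2−f)
- Part after the restart = 2(1−f)T
- Restart rate for a whole infusion of 120 min = (1−f)T/(120−fT)
- Restart rate for the remainder alone to last 120 min = (1−f)T/120

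| T (min) | f | Whole (min) | After restart (min) | Rate needed, whole | Rate needed, remainder |
|---|---|---|---|---|---|
| 30 | 0.1 | 57 | 54 | 23% | 22.5% |
| 30 | 0.5 | 45 | 30 | 14% | 12.5% |
| 30 | 0.9 | 33 | 6 | 3% | 2.5% |
| 60 | 0.1 | 114 | 108 | 47% | 45% |
| 60 | 0.5 | 90 | 60 | 33% | 25% |
| 60 | 0.9 | 66 | 12 | 9% | 5% |

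Once any drug has been given, a half-rate restart stays below 120 min, whether the row's time means the whole infusion or the remainder. It reaches 120 min only at T = 60 and f = 0.

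If the row covered later doses only, these figures would not apply to a same-day restart. Table 5 would then set no Grade 3-specific condition for that restart at all. Either way the text needs a clarifying sentence.

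**Reach**

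Section 2.3.2 reports IRRs in 21% of participants at 2.5 mg/kg in the global phase II study, Grades 1 to 3, mostly at the first infusion. For a cohort of 6, 6 × 0.21 = 1.26 participants with any IRR. The Grade 3 share is not given. Assuming 5% to 40%, the expected number with a Grade 3 reaction is 1.26 × 0.05 = 0.06 to 1.26 × 0.40 = 0.50.

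**The case against.** The strongest reply is that a careful reader gets this right. The Grade 3 row is specific and restrictive, footnote b is permissive, and 6.1.1 qualifies its halving as a general rule, which leaves room for an exception. This stands as far as it goes: the row is the better reading. A reader might infer that footnote b overrides the row and licenses a half-rate restart after a Grade 3 reaction. The documents do not support that. They leave the order of precedence unstated.

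The site can also find the right rules. Table 5 follows Table 4 in Section 6.6, whose opening lines name Tables 5 and 6 for adverse events. The risk table in 2.4.1 sends IRR management to Sections 6.6 and 7.1.4, and 7.1.4 names Table 5. This also stands and limits the harm, although the pointer in 6.1.1 is still wrong. For 8.3.8, a reader might infer that the reference to Table 4 is empty. It is not: Table 4 defines the reduction levels on which Table 5 relies. The reference is incomplete, because Table 4 has no interruption or toxicity-specific rule.

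Other sections give partial protection. Section 7.1.2 states: "A participant that exhibits signs or symptoms of severe hypersensitivity or anaphylaxis will receive appropriate medical treatment and permanently discontinue study treatment". Section 8 adds: "Immediate safety concerns should be discussed with the sponsor immediately upon occurrence or awareness". Neither sets premedication or infusion time for other Grade 3 reactions.

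Finally, the current amendment mentions two ongoing participants, who are past the first infusion, when most reactions occur. For them the expected number is below the range above. New first infusions nevertheless remain possible, because the 3.4 mg/kg cohort is optional (4.1.1) and the Dose Escalation Committee may request more participants at completed levels (9.5.2).

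**Conclusion.** Wrong as written, of minor severity. An operative dosing instruction conflicts with the Grade 3 row of its own table, and 6.1.1 cites a table without the content it promises. The conflict is one of substance: from the halfway point a half-rate restart gives 45 to 90 minutes in all, against a minimum of 120. It is an unresolved precedence, best read in favour of the Grade 3 row.

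The size in participants is small. The 21% comes from another study at 2.5 mg/kg, and the Grade 3 share of 5% to 40% is an assumption, so 0.06 to 0.50 of 6 only illustrates scale. Section 2.3.2 does show that the event is real: one participant at 2.5 mg/kg stopped treatment after Grade 3 reactions at the first and second infusions. No sample size, estimate or planned analysis is affected.

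**What to change.** 1. In footnote b, limit only the 50%-rate restart sentence to Grade 2 or lower. Keep its second rule for all grades at which restart is possible: if symptoms do not resolve within one hour, hold dosing to the next scheduled dose and premedicate. Limiting the whole footnote to Grade 2 would remove that hold at Grade 3 and leave Grade 1, which has no row in Table 5, without a rule.
2. In the Grade 3 row, add that its conditions apply to any restart, including on the same day, and that a same-day restart is allowed only if symptoms resolve within one hour.
3. In 6.1.1, except Grade 3 from the halving sentence, note that Grade 4 is discontinued, and change Table 4 to Table 5.
4. In 8.3.8, add Tables 5 and 6 to the Table 4 reference and keep Table 4.

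The cost is protocol wording only, with ethics committee review if it is handled as an amendment (11.1.1). Visits, sample size and analysis do not change.

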6.6.1. Corneal Supportive Care Guidelines for Belantamab Mafodotin

Changes in visual acuity, which commonly manifests as changes in corneal epithelium observed on ocular examination, have been observed with antibody drug conjugates, including those conjugated to MMAF [Eaton, 2015].

Sites are required to establish a close collaboration with an ophthalmologist (or optometrist, if an ophthalmologist is not available) who will be responsible for assessing participants and managing those who develop corneal epithelium on ocular examination in close communication with GSK Medical Monitor.

Participants will be assessed by an ophthalmologist (or an optometrist if an ophthalmologist is not available) baseline and every three weeks. If there are no corneal examination findings (Grade 2 or above) at time of the Cycle 6 exam, participants may

have their ophthalmologic exams decreased to once every 3 months. In case of persistent ocular exam findings, newly developed ocular symptoms or vision changes, further ocular exams should be performed at least every cycle until resolution (to Grade 1 or baseline) or more frequently as clinically indicated by the qualified eye care specialist (Appendix 9). See Section 8.3.9 for the list of ophthalmic exam procedures.

Participants who have ocular symptoms at end of study treatment will continue to be followed as indicated in the SoA (Section 1.3) for up to 12 months, or until full resolution of findings: defined as a return to participant's baseline, or until deemed clinically stable by an ophthalmologist (or an optometrist if an ophthalmologist is not available), whichever comes first. Clinically stable is defined as changes less than or equal to Grade 1 as per Table 7.

Prophylactic preservative-free artificial tears should be administered in each eye at least 4 to 8 times daily, beginning on Cycle 1 Day 1 until EOT. Allow at least 5-10 minutes between administration of artificial tears and steroid eye drops (if administered). In the event of ocular symptoms (e.g., dry eyes), the use of artificial tears may be increased up to every 2 hours as needed.

While not yet clinically demonstrated, it is possible that the application of a cooling eye mask during belantamab mafodotin administration, and in the first few hours after infusion may subsequently decrease ocular side effects. On the day of infusion, at the discretion of the participant and the investigator, the following may be considered:

- Beginning with the start of each belantamab mafodotin infusion, participants may apply cooling eye masks for approximately 1 hour or as much as tolerated.
- Participants may continue using the cooling eye mask beyond the first hour for up to 4 hours. Further use beyond 4 hours is at the participant's discretion.

Prophylactic or therapeutic corticosteroid eye drops are not required but can be used if clinically indicated. An ophthalmology (or optometry, if ophthalmology is not available) consult is required for all participants who require steroid eye drops for more than 7 days.

Participants must avoid the use of contact lenses during the study. An ophthalmology/optometry consult is required for all participants who develop signs or symptoms of corneal toxicity.

A summary of prophylactic interventions for corneal toxicity associated with belantamab mafodotin is provided in Table 8.

Table 8 Prophylactic measures for corneal toxicity associated with belantamab mafodotin ^a

Prophylactic		
Measurea	Dose and Administration	Timing
Preservative-free	Administer in each eye at least 4	Administer daily beginning on Cycle 1
artificial tears	to 8 times daily	Day 1 until EOT. Allow 5-10 minutes
		between administration of artificial tears
		and steroid eye drops (if administered)
Cooling eye mask	May apply cooling eye mask to	During belantamab mafodotin infusion
	both eyes for approximately	administration in the first hour for up to 4
	1 hour or as much as tolerated	hours, as tolerated

a. Dose modifications and treatment for ocular toxicities are discussed in Section 6.6

6.7. Intervention after the End of the Study

The investigator is responsible for ensuring that consideration has been given to the post-study care of the participant's medical condition.

Refer to Section 8 and the SOA (Table 1) for follow-up assessments of participants who are to be followed for disease progression after they permanently discontinue from study treatment.

7. DISCONTINUATION OF STUDY TREATMENT AND PARTICIPANT DISCONTINUATION/WITHDRAWAL

7.1. Discontinuation of Study Treatment

Participant will receive study treatment until disease progression, death or unacceptable toxicity (including but not restricted to meeting stopping criteria for significant toxicity as outlined in Section 6.6), loss to follow-up, or end of study (Section 4.4).

The study treatment must be permanently discontinued for any of the following reasons:

- disease progression or unacceptable toxicity (including protocol-defined safety stopping criteria)
- Pregnancy

Study treatment may be permanently discontinued for any of the following reasons:

- deviation(s) from the protocol
- request of the participant or proxy (withdrawal of consent by participant or proxy)
- Investigator's discretion
- concurrent illness that prevents further administration of study treatment(s)
- participant is lost to follow-up

study is closed or terminated.

The primary reason of study treatment was permanently discontinued must be documented in the participant's medical records and electronic case report form (eCRF).

If the participant voluntarily discontinues from treatment due to toxicity, AE must be recorded as the primary reason for permanently discontinuation on the eCRF.

Once a participant has permanently discontinued from study treatment, the participant will not be allowed to re-enter the study.

All participants who discontinue from study treatment for any reason other than confirmed progression or death will complete safety assessments, and will be followed up for PD after study as specified in the SoA (Table 1).

PD Follow-up:

All participants who permanently discontinue study treatment in the absence of disease progression will remain in the study and will be followed for progression according to the protocol schedule until:

- Progression is documented, or
- New anti-cancer therapy is initiated, or
- Lost to follow-up, or
- Withdrawal of consent, or
- Death occurs, or
- End of study (Section 4.4)

[figure not shown]
